APPENDIX 3. OVERVIEW OF RESEARCH SITES

21

GLOSSARY OF ABBREVIATIONS

CLOCS	Cancer Loyalty Card Study
HSR1	High Street Retailer 1
HSR2	High Street Retailer 2

KEYWORDS

Ovarian Cancer
Epidemiology
Observational Study
Risk Assessment

STUDY SUMMARY

TITLE Cancer Loyalty Card Study (CLOCS)

DESIGN Observational, retrospective case-control study

AIMS The CLOCS aims to investigate whether or not women have distinctive self-management behaviours prior to seeing their doctor with symptoms that are associated with ovarian cancer.

OUTCOME MEASURES The primary outcome of the CLOCS will be to define the time by which the cases and controls are statistically significantly different in their purchase behaviours leading up to diagnosis on a population level.

The secondary outcome of the CLOCS will be defining a purchase threshold as an “alert” about cancer symptoms in individuals and determining the predictive utility of purchasing behaviours in the early detection of ovarian cancer. Exploratory analyses will include longitudinal analyses, frequency of purchases and an unbiased analysis of other purchase categories.

POPULATION At least 1000 women in the UK (500 ovarian cancer cases and 500 controls)

ELIGIBILITY Women, at least 18 years old, who own at least one participating high street retailer loyalty card are eligible to join the CLOCS. Among these women, those who have been diagnosed with ovarian cancer can join the CLOCS as cases, and those who have no prior ovarian cancer diagnosis are eligible to join as controls.

DURATION 3 years

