1. INTRODUCTION

1.1 BACKGROUND

The ten-year survival rate for epithelial ovarian cancer (EOC) is only 35% in the UK and is dramatically different for stage 1 disease (90%) compared with stage 3-4 (5-15%). Survival in the UK lags behind Europe; this is attributed partly to a delay in diagnosis [1]. Earlier detection of low-volume disease or earlier stage ovarian cancer will save lives [2].

EOC is a heterogeneous disease with different histological subtypes that show strikingly different molecular [3] and mutational profiles [4,5]. With the Ovarian

Cancer Association Consortium (OCAC), we have identified 34 common genetic polymorphisms contributing to polygenic risk [6–9]. Epidemiological risk factors provide a predictive model with a modest discriminatory power (AUC=0.65), improved slightly with polygenic risk (AUC=0.66) [10], and this model has been proposed to improve EOC detection with risk stratified screening [11].

EOC usually presents with vague and non-alarming symptoms. As a result, most women are diagnosed late when the cancer has already spread and the prognosis is poor. The most common symptoms associated with EOC are increased abdominal size, pelvic pain, abdominal pain and bloating, feeling full quickly and difficulty eating [12,13]. The major reasons for not presenting to the GP with symptoms such as these are “not wanting to waste the GP’s time” [14] and normalisation of these symptoms [15]. The persistence of a symptom, social influence and awareness encourage help-seeking behaviours in primary care [16]. However, few believe that their symptom(s) might be a sign of cancer [17]. Consequently, people might choose to self-manage their symptoms by using over-the-counter medication, and to seek advice from other sources, (pharmacists, family, internet), rather than a primary care physician.

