2. STUDY OBJECTIVES

- 2.1** The primary aim of the CLOCS will be to define the time by which participants with ovarian cancer are statistically significantly different in their purchase behaviours leading up to date of diagnosis, compared with purchase behaviours of participants without ovarian cancer.
- 2.2** The secondary aim of the CLOCS will be to define a purchase threshold as an “alert” about cancer symptoms in individuals and determining the predictive utility of purchasing behaviours in the early detection of ovarian cancer.

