3.1 STUDY OUTCOME MEASURES

We aim to detect significant changes in purchase behaviours of ovarian cancer patients prior to diagnosis, and potentially improve the sensitivity of detection of cancer “alert symptoms” by stratifying the analysis on risk profiles, cancer stage or histology.

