6. OVARIAN CANCER RISK FACTOR AND SYMPTOM DATA COLLECTION

6.1 Upon choosing to participate in the CLOCS, participants will also complete a questionnaire requesting information about well-established ovarian cancer risk factors and symptoms.

6.1.1 The well-established risk factors include ethnicity, marital status, body mass index, age at menarche, menopausal status, age at menopause, parity,

breastfeeding, hysterectomy, tubal ligation, cancer history, endometriosis, aspirin use, oral contraceptive use, hormone replacement therapy (HRT), family history of ovarian and breast cancers, vaping, and cigarette smoking

- 6.1.2** The questionnaire asks participants about the symptoms experienced (if any) and number of visits to the general practitioner in the year leading up to cancer referral or diagnosis.
- 6.1.3** The questionnaire asks participants about which food and pharmacy stores they shop at regularly, at which stores they own a loyalty card, frequency of use of those loyalty cards, where they heard about the study (for controls only), and the number of people in their household (for adjustment in analysis).
- 6.1.4** In order to understand the impact of COVID-19 on purchase history and ovarian cancer diagnosis delays, the questionnaire includes a question about whether participants have had Covid19 (diagnosed and recovered/diagnosed and still ill/suspected but not formally diagnosed/did not have covid)
- 6.1.5** For participants diagnosed with ovarian cancer (considered cases), this will occur in the clinic or at home if they choose to complete it at home.
- 6.1.6** For participants who do not have ovarian cancer (considered controls), this questionnaire will be completed online.
- 6.2** For participants with ovarian cancer, there will be a separate questionnaire to be completed by their recruiting clinician or member of their healthcare team regarding information about ovarian cancer diagnosis date, type, grade, stage, and surgical outcome, if any. If a patient chooses to complete the questionnaire at home, a member of the clinical care team will send their completed clinical questionnaire with them.
- 6.3** The clinical care teams will not keep a copy of the CLOCS participant consent form.

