9.2 Data analysis

- 9.2.1 The statistical software R will be used for all data analyses.
- 9.2.2 We will define the time prior to diagnosis by which the cases become statistically significantly different in their purchase behaviours to the controls.
- 9.2.3 We will explore this using a multivariable, conditional logistic regression model with ovarian cancer as the outcome and "purchase proportion" at different times prior to diagnosis as the exposure, adjusting for stage and histology and other potentially confounding variables collected from the risk factor questionnaire.
- 9.2.4 We will compare the proportions of purchases in cases to controls, stratified by risk quintiles defined by the epidemiological risk model (estimated n=86 per quintile) or by histology (with expected proportions of high grade serous cases n=335; mucinous cases n=70; endometrioid n=35; clear cell n=35, and low grade serous n=25).
- 9.2.5 We will estimate the predictive values (ROC AUC, PPV, NPV, specificity and sensitivity) of this "early diagnosis" test for each stratum.
- 9.2.6 We will conduct exploratory analyses investigating other methods leveraging the auto correlation in the longitudinal data. Specifically, we will investigate the frequency of purchases and purchase trajectories, to identify purchase patterns (e.g. increasing purchases before diagnosis, purchase peaks, etc.), that are indicative/predictive of the individual disease onset.

- 9.2.7** Using longitudinal approaches, we will investigate if these patterns help in predicting the time-to-onset.
- 9.2.8** This type of approach could be generalised using other purchase categories for further hypothesis generation.

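### The purchase alert's window and threshold are derived in the same women who supply its accuracy estimates, with no internal validation described, so section 9.2.5 as written yields apparent accuracy

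*Combined protocol and SAP*

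**What the plan says.** Under outcome measures, the study summary states: "The secondary outcome of the CLOCS will be defining a purchase threshold as an" alert about cancer symptoms in individuals. Aim 2.2 pairs that with "determining the predictive utility of purchasing behaviours in the early detection of ovarian cancer". Both belong to one study with one set of women: at least 500 cases and 500 controls.

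Section 9.2.2 takes the time window from those women: "We will define the time prior to diagnosis by which the cases become statistically significantly different in their purchase behaviours to the controls". Section 9.2.3 explores this with a multivariable conditional logistic model, using the purchase proportion at several times before diagnosis as the exposure. Section 9.2.4 stratifies by risk quintile (n=86 each) or by histology (335, 70, 35, 35 and 25 cases). Section 9.2.5 will then "estimate the predictive values (ROC AUC, PPV, NPV, specificity and sensitivity) of this" test for each stratum.

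Section 9.2 does not say how the threshold is set. That it comes from the study data is a reading of aim 2.2 and the study summary. The only mention of validation concerns identity checks on controls (9.1.6b). The proof-of-concept study is cited for the website approach (5.1), not as a source for a window or cut-off.

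**The concern.** A rule chosen because it separates these cases from these controls will, on average, separate them better than it separates new women. The mechanisms differ by measure. Choosing the window, or fitting any model that feeds the score, pushes AUC up. Choosing the cut-off leaves AUC alone but can push up the sum of sensitivity and specificity, by an amount that depends on the cut rule.

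At stake is a named secondary outcome. If purchases carried no information, the uncorrected figures would still look mildly favourable. Section 1.1 describes the step from AUC 0.65 to 0.66 as a slight improvement, so an overstatement of 0.02-0.03 exceeds a difference the protocol itself remarks on.

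**Working it through.** **The plan's own figures.** The documents state no expected AUC, significance level, power or sample-size derivation, so there is no accuracy figure to reproduce. The histology strata add up: 335 + 70 + 35 + 35 + 25 = 500 cases. The quintiles do not: 5 x 86 = 430. That gap does not affect this point.

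**Inputs from the documents.** 500 cases and 500 controls (study summary); strata of 86 and 25 (9.2.4); several candidate times (9.2.3, number not given).

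**Assumed inputs.** Purchases per window Poisson with mean 1; 12 or 24 windows; correlation between windows 0 or 0.5; 86 read as cases. The window with the highest AUC is chosen, standing in for the plan's significance rule. Where there is a signal, the case mean rises over the last quarter of windows to 1.349 (AUC 0.585) or 1.658 (AUC 0.65).

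**Definitions.** AUC = P(case count > control count) + 0.5 x P(tie). Optimism = apparent value in the study women minus the true value of the chosen rule.

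**One common test, 500 v 500, AUC optimism:**

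| Signal | 12 windows, r=0 | 12, r=0.5 | 24, r=0 | 24, r=0.5 |
|---|---|---|---|---|
| none | 0.028 | 0.022 | 0.034 | 0.025 |
| peak 0.585 | 0.005 | 0.002 | 0.013 | 0.008 |
| peak 0.65 | 0.001 | -0.001 | 0.008 | 0.003 |

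This gives 0.02-0.03 with no signal and 0.00-0.01 with one.

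**Sensitivity plus specificity, same setting, no signal.** 0.04-0.06 if the cut maximises the sum; about 0.01-0.02 if the cut is set at 90% specificity.

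**Other assumptions, common test.** In a separate simulation (normal scores, 12 windows, correlation 0.5) with the same true AUC of 0.60 in every window, apparent AUC is 0.626, an optimism of 0.626 - 0.600 = 0.026. The small figure with a signal therefore depends on the signal being concentrated near diagnosis. With no signal and 72 windows, apparent AUC is 0.542, an optimism of 0.042.

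**Only if the window is re-chosen within each stratum, AUC optimism with no signal:** 86 v 86, 0.05-0.08; 25 v 500, 0.07-0.11; 25 v 25, 0.09-0.15. With a peak AUC of 0.65 these become about 0.01-0.04, 0.03-0.06 and 0.05-0.10.

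**Only if the score is a fitted model** of the 18 factors listed in 6.1.1 plus one purchase term, with true AUC 0.65 (the value section 1.1 gives for the epidemiological risk model): 0.665 - 0.633 = 0.032 at 500 v 500, and 0.720 - 0.585 = 0.135 if refitted at 86 v 86.

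**Does the remedy work?** Cross-validation that keeps pairs together and re-chooses window and cut in each fold gave an AUC within -0.003 to 0.002 of the truth at 500 v 500, -0.015 to 0.011 at 86 v 86, and -0.022 to 0.004 at 25 v 25.

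**PPV, a separate matter.** PPV = sens x p / [sens x p + (1 - spec) x (1 - p)]. With sensitivity and specificity of 0.6:
- at the study's 1:1 ratio (p = 0.5), 0.30 / (0.30 + 0.20) = 0.60;
- at an assumed p = 0.001, 0.0006 / (0.0006 + 0.3996) = 0.0015.

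**The case against.** The best case for the plan is that it describes one test. Section 9.2.5 speaks of a single test applied to each stratum, and the primary outcome concerns differences "in their purchase behaviours leading up to diagnosis on a population level". With one common window and a real signal near diagnosis, AUC optimism is 0.00-0.01, which hardly matters. An alert might well be set at a target specificity, and then optimism from the cut is small too. Under the plan's significance rule there might also be no test to evaluate if there were no signal: with independent windows each tested at an assumed unadjusted two-sided 5%, none is significant with probability 0.95^12 = 0.54 or 0.95^24 = 0.29.

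Most of this stands as an argument about size. It does not remove the omission. Whether there is a signal is what the study sets out to learn, so the no-signal case cannot be set aside. On the same arithmetic a false window would be found in 46% to 71% of such studies.

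Two stronger readings are tempting. Section 3.1 hopes to improve sensitivity "by stratifying the analysis on risk profiles, cancer stage or histology", from which a reader might infer that window and cut are re-chosen in each stratum and that the within-stratum figures apply. No passage says so. A reader might also infer that the 9.2.3 model is the alert score. That section uses the model to explore timing with adjustment, aim 2.2 concerns a purchase threshold, and 9.2.4 uses the risk model only to form strata. Nor can one say that choosing a threshold must materially inflate sensitivity plus specificity, because that depends on a cut rule the plan does not give.

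**Conclusion.** The concern holds in a limited form. The window and, on the natural reading of aim 2.2, the threshold are derived in the women who supply the accuracy estimates. The available text describes nothing to correct for that, so as written the secondary outcome would be apparent accuracy.

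On the most natural reading the bias is modest, as set out in the working: a few hundredths of AUC with no signal, and about 0.01 or less with a signal concentrated near diagnosis. The within-stratum and model-fitting figures are conditional and should not be quoted as the expected bias. All sizes rest on assumed purchase rates, window counts and correlations, and on the highest-AUC window replacing the significance rule. The finding covers only the text available for review.

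**What to change.** In section 9.2.5:

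1. Repeat every data-driven step (window choice, threshold choice, any model fitting that feeds the score) inside cross-validation folds that keep matched sets together, or inside an optimism bootstrap. This requires the cut rule to be written down, along with whether one window serves all strata.
2. Report optimism-corrected AUC, sensitivity and specificity with confidence intervals, overall and by stratum, and label any uncorrected value as apparent.
3. As a separate change, derive PPV and NPV from the corrected sensitivity and specificity at a stated population prevalence, since the 1:1 ratio does not give a usable PPV.

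The cost is extra analysis code and a few sentences; no new data are needed. AUC, sensitivity and specificity will look slightly less favourable, PPV will be much lower, and corrected estimates in the smallest strata will be imprecise.

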10. REGULATORY ISSUES

10.1 ETHICS APPROVAL

The Chief Investigator has obtained approval from the North West - Greater Manchester South Research Ethics Committee (19/NW/0427). The study must also receive confirmation of capacity and capability from each participating NHS Trust before accepting participants into the study. The study will be conducted in accordance with the recommendations for physicians involved in research on human subjects adopted by the 18th World Medical Assembly, Helsinki 1964 and later revisions.

10.2 CONSENT

Consent to enter the study must be sought from each participant only after a full explanation has been given, an information leaflet offered and time allowed for consideration. Signed participant consent should be obtained. The right of the participant to refuse to participate without giving reasons must be respected. After the participant has entered the study the clinician remains free to give alternative treatment to that specified in the protocol at any stage if he/she feels it is in the participant's best interest, but the reasons for doing so should be recorded. In these cases the participants remain within the study for the purposes of follow-up and data analysis. All participants are free to withdraw at any time from the protocol treatment without giving reasons and without prejudicing further treatment.

10.3 CONFIDENTIALITY

The Chief Investigator will preserve the confidentiality of participants taking part in the study and is registered under the Data Protection Act.

Any CLOCS documents in paper form will be kept in a locked cupboard in a locked office within a locked department in the Imperial College main study site, and only the chief investigator will have access.

All data are kept in the Secure Enclaves, an isolated environment within Imperial College network. It is split into two main sections, one for holding identifiable data, and the other for de-identified research data. It was created to give Imperial College assurance that groups holding personal health data were compliant with all their processing requirements. All access into the enclaves is controlled and audited by the Security Manager and Quality Assurance Officer. The environment is Data Security and Protection Toolkit compliant and ISO27001 certified.

Data Handling and Security

The CLOCS research team is committed to protecting the confidentiality of data. Systems have been established for the secure data flow and storage of data to protect confidentiality. All identifiable information, including contact details will remain secure at the research site. A masterfile, allowing re-identification and linkage will be managed by [name], the CLOCS chief investigator. The access to de-identified data within Imperial College will be limited to approved researchers.

Secure Operating Environments

All data will be stored and processed in the College's ISO27001 certified secure environment – the "Secure Enclave". This is a fully managed infrastructure and secure environment providing high availability, resilience and business continuity through multiple servers, back-ups and disaster recovery measures.

A robust data security model has been designed to protect sensitive personal and medical data from the potential risk of unauthorised access or distribution. All information input, viewed or extracted is protected so that only users with the correct authority and access can create, view, amend or delete information. Access to the system will be governed by authentication and authorisation privileges that will check:

- Access is by an authorised person and the user is who they say they are. This is controlled by a username and complex password;
- The user accessing the system is authorised to do what they are attempting to do. That includes searching, updating, deleting and uploading information at the appropriate authorised level for the database(s) or table(s).

In summary, the security architecture provides the optimal level of protection available through implementing best practice network, hardware, software and data security measures.

Participant identity will be linked to the analysis datasets only through a unique barcode assigned when completing the recruitment questionnaire, meaning the data will be pseudonymised. The only identifiable information will be on the consent form along with the participant barcode. Retailer data and questionnaire data will only be linked via the pseudonymised participant barcode. The only person with access to the link between participant identity and the barcode is the chief investigator and this information will be kept in a locked cupboard (paper form) and on the secure encrypted server (electronic form). All researchers on the study team understand all data is confidential.

10.4 INDEMNITY

Imperial College London holds negligent harm and non-negligent harm insurance policies which apply to this study.

10.5 SPONSOR

Imperial College London will act as the main Sponsor for this study. Delegated responsibilities will be assigned to the NHS trusts taking part in this study.

10.6 FUNDING

Cancer Research UK are funding this study under the Cancer Research UK Early Diagnosis Project Grant (C38463/A26726).

The study may be subject to inspection and audit by Imperial College London under their remit as sponsor and other regulatory bodies to ensure adherence to GCP and the UK Policy Frame Work for Health and Social Care Research.

11. STUDY MANAGEMENT

The day-to-day management of the study will be co-ordinated through the CLOCS research team.

12. PUBLICATION POLICY

At the end of the study, we aim to publish results of findings in peer-reviewed journals and present them at conferences. Extra care will be taken to ensure no participants are identifiable in any of the dissemination. The final study report will be produced summarising the information we have learned and will be hosted on the study website.

